**Protocol:**

**Informed Consent:**

Subjects must have read the contents of the written informed consent document, had all questions regarding the study adequately answered by study staff, and signed and dated the document prior to any study related activities.

**14/16 (TAVR) French Control patients:** Patients will have a Perclose™ device deployed at the arteriotomy. Manual pressure will be held for at least 5 minutes, the beginning of which will correspond to time point zero. Patent hemostasis will be documented after device deployment. Any manual compression needed or per protocol under the discretion of the operator will count towards the time to hemostasis. After hemostasis is achieved in the cath lab the patient will be sent to the post-operative area and monitored for further bleeding or hematoma formation as described previously.

**14/16 (TAVR) French Statseal Protocol:** Patients will have a Perclose™ device deployed at the arteriotomy. A Statseal Advance (SS) disc will applied with 2 piece of gauge over it and manual pressure will be held for at least 5 minute, the beginning of which will correspond to time point zero Patent hemostasis will be documented after device deployment. Any manual compression needed or per protocol under the discretion of the operator will count towards the time to hemostasis. After hemostasis is achieved in the cath lab, the patient will be sent to the post-operative area and monitored for further bleeding or hematoma formation as described previously.

*[rest of page intentionally blank]*

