### **III. STUDY OBJECTIVE(S)**

The primary objectives of this study are to evaluate the performance of StatSeal Advanced used in conjunction with the Perclose™ (SS) as compared to the Perclose™ without SS (PC) relative to:

TAVR Outcomes:

1. Primary outcome: Time to Hemostasis (TTH)
2. Secondary outcome: The incidence of access hematomas

Time to hemostasis (TTH) is defined as the time period required to achieve hemostasis, beginning at the time at which the Perclose™ is deployed to the access site to when no additional bleeding is appreciated..

Hematoma are defined as being <5 cm, 5-10 cm, and >10 cm. The physician on the study team will make the assessment for the incidence and size of the hematoma based on physical exam and /or diagnostic imaging including ultrasound. Hematoma assessment will be done in multiple incidences: at the time of Perclose deployment while in the catheterization lab, at the time of admission to the recovery unit by the TAVR team, and at the time of admission to the inpatient service for overnight monitoring. While in recovery the patient will be evaluated by the staff for 15 minutes for one hour, every 30 minutes for the next hour, and every hour for the subsequent four hours (for a total of 6 hours post-procedure while in the recovery unit). While admitted for overnight monitoring (at least for a 24 hour period), the patient will have their site evaluated every 4 hours until the 24 hours period has been reached.

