#### **STUDY METHODS:**

Patient Selection Criteria Study subjects will be identified in their outpatient appointments during their appointments with the structural heart team prior to their TAVR procedure.

Inclusion Criteria:

- Left heart catheterization with plans for delivery of a 14-16 Fr TAVR system

Exclusion Criteria:

Candidates for this study will be excluded if any **one** of the following criteria is true.

- Use of a hemostasis method or device besides Perclose™ (Perclose may not be used in situations of heavy calcification, presence of dissection, etc).
- Use of an anticoagulant other than unfractionated heparin or bivalirudin during the procedure.
- Any use of glycoprotein inhibitors or cangrelor.
- Use of sheathless guides.
- Any anticipated need for continued anticoagulation post-catheterization, including extended bivalirudin infusion.
- Any active treatment with oral anticoagulants continued during course of procedure.
- Presence of arteriovenous dialysis fistula in the ipsilateral leg.
- Any physical deformity or trauma / injury of the leg that would prevent proper placement or function of the hemostasis band.
- Inability of the patient to personally consent for the study. (no surrogate consent)
- Cardiogenic shock, emergent procedures (high risk myocardial infarctions), or any clinical instability as assessed by the physician performing the procedure.

Transfemoral Catheterization Procedure

TFA Cardiac Catheterization will be performed according to local practice standards with use of a 14-16 Fr sheath during a TAVR procedure.

Patients will have their activated clotting time measured prior to sheath removal and at least 5 minutes following the initial dose of anticoagulant. Additional activated clotting time measurements for PCI would be expected as part of routine practice but not recorded. Vasodilators (nitroglycerin, verapamil) will be administered in accordance with local practice.

Timing of Subject Enrollment

A subject will be consented into the study prior to the administration of sedation prior to the procedure, and randomized at the conclusion of a successful deployment of the Perclose device (after all anticoagulation and antiplatelet medication decisions have been made), at which time placement of the assigned device will occur. Eligibility for the study will be assessed at this time and the subject will have to meet all of the inclusion criteria and none of the exclusion criteria.

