Randomization will be performed by means of sealed envelopes in randomization blocks of 25. Each envelope will be labeled by patient number containing device designation. Device designation in the envelopes will be random in occurrence. When a patient is officially enrolled (after Perclose™ deployment) the envelope corresponding to that patient number in the Study Patient log will be pulled, opened, and the assignment revealed.

End of Study Status / Effect of Withdrawals:

A subject will have completed the study when one of the following events is documented:

1. The patient is successfully enrolled, treated with a Perclose™, and completes all required follow up.

2. A subject withdraws consent to participate. Patients who withdraw from the study will have their data included to the extent allowable by law. As all study related procedures are expected to be completed on the day of the procedure or day after, subject withdrawal is not considered likely.

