#### Primary Efficacy Outcome:

- Total Time to Hemostasis (TTH), defined as from the time of manual compression after Perclose™ deployed until no further bleeding..

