### **VI. STUDY STATISTICAL PLAN:**

This is a physician initiated, prospective, randomized, two-arm study, to be conducted at high-

volume academically affiliated centers with the cath lab staff having a (minimum) ten case experience using StatSeal Advanced. The primary analysis will be by intention-to-treat methodology.

A sample size of 50 patients is sufficient to have >90% power to detect an average expected difference of 10 minutes in time (5 min vs 15 min) to hemostasis (different primary outcomes compared to 6F study) between the SS and Perclose groups, using a two-sided alpha of 0.05. A standard deviation of 10 minutes is assumed, which will be the additional time for manual compression if any site oozing/bleeding is seen after the initial compression. A different standard deviation time was assumed given larger bore access for TAVR TFA access.

Descriptive summary statistics will be presented for all study variables. Continuous variables will be displayed as means with standard deviations and medians with 75th and 25th percentiles. Categorical variables will be summarized as frequencies with their respective percentages with two-sided 95% exact confidence intervals of the percentages. Statistical comparisons for continuous variables will be performed using the Student's t test or Mann-Whitney U test, as appropriate. Comparisons for categorical variables will be performed using the Chi square test or Fisher exact test, as appropriate. A two-sided P value of 0.05 will be considered statistically significant.

A single multivariate logistic regression will be reported for the safety outcome of hematoma formation. In order to create this model, study arm and variables known to place patients at higher risk for hematoma formation will be tested in univariate analysis for the primary safety outcome. Those variables with a P<0.10 will be included in backwards stepwise regression modeling to obtain a final model. Similar to our prior published study, the following variables will be analyzed: Age, sex, weight, hypertension, diabetes, creatinine, pre-procedural INR, pre-procedural platelet level, heparin dose given, PCI, last ACT prior to procedural end, and last SBP prior to procedural end.

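### Time to hemostasis, the primary outcome, has two start times, with a StatSeal-only step between them, and it is unclear whether the minimum hold counts once bleeding has stopped

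*Combined protocol and SAP*

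**What the plan says.** **Start of the clock.** Section III (Study Objectives) defines TTH as the period "beginning at the time at which the Perclose™ is deployed to the access site to when no additional bleeding is appreciated". Section V (Primary Efficacy Outcome) has it "defined as from the time of manual compression after Perclose™ deployed until no further bleeding". The control-arm description in Section IV agrees with Section V: "Manual pressure will be held for at least 5 minutes, the beginning of which will correspond to time point zero". The StatSeal description uses the same time zero, but the "disc will applied with 2 piece of gauge over it and manual pressure will be held for at least 5 minute", so the disc is on before the clock starts.

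**What lies between the two starts.** Section IV (Timing of Subject Enrollment) randomizes once the Perclose has been deployed successfully, "at which time placement of the assigned device will occur". The randomization paragraph adds that after deployment "the envelope corresponding to that patient number in the Study Patient log will be pulled, opened, and the assignment revealed".

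**End of the clock.** Sections III and V stop TTH when no more bleeding is seen. Section IV adds, identically for both arms: "Any manual compression needed or per protocol under the discretion of the operator will count towards the time to hemostasis".

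**Planning assumptions.** Section VI assumes means of 5 and 15 minutes and a standard deviation of 10 minutes, "which will be the additional time for manual compression if any site oozing/bleeding is seen after the initial compression". It claims more than 90% power with 50 patients at two-sided alpha 0.05. It does not say which start the means are measured from.

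**The concern.** Two people who each follow the protocol can record different primary-outcome values for the same patient, and nothing says which definition governs. The start times do not differ by a harmless constant, because disc and gauze placement falls between them in the StatSeal arm only. Under the Section III clock that step is charged to StatSeal and shrinks any advantage it has. The unclear stop matters because the minimum hold has the same length as the mean assumed for StatSeal. Whether the hold counts therefore decides whether the planning assumptions are possible at all. Times not noted during the procedure may not be recoverable later.

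**Working it through.** **1. The plan's own figure.** Inputs from Section VI: difference 15 − 5 = 10 min, SD 10 min, two-sided alpha 0.05, 50 patients. The allocation ratio is not stated, so 25 per arm is assumed.

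For a two-sample t test, noncentrality = d / (SD × √(2/n)) with 2n − 2 degrees of freedom. Here √(2/25) = 0.283, so 10 / (10 × 0.283) = 3.54 with 48 degrees of freedom. Power is 93.4% (94.2% by the normal approximation). The stated figure is reproduced.

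**2. Order of events.**

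| Event | Control | StatSeal |
|---|---|---|
| Perclose deployed | Section III clock starts | Section III clock starts |
| Envelope opened | Yes (that it precedes pressure is implied, not stated) | Yes (must precede the disc) |
| Disc and gauze placed | No | Yes |
| Manual pressure begins | Section IV and V clock starts | Section IV and V clock starts |

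A delay common to both arms leaves the difference at 10 min and adds only variability. With an assumed added SD of 1 to 3 min, the total SD is √(100 + 1) = 10.05 to √(100 + 9) = 10.44, and power is 93.2% to 91.3%. Envelope opening is therefore not the issue. The disc step is.

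**3. Effect of a StatSeal-only step on the Section III clock.** The step length is an assumption, since the documents give none. The 10-min difference is taken as measured from the start of compression.

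| Step (min) | Difference (min) | Noncentrality | Power (t test) |
|---|---|---|---|
| 0 | 10 | 3.54 | 93.4% |
| 0.5 | 9.5 | 3.36 | 90.8% |
| 1 | 9 | 3.18 | 87.7% |
| 2 | 8 | 2.83 | 79.2% |

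**4. The stop.** Take a StatSeal patient with 1 min between deployment and compression, whose bleeding stops 3 min into a 5-min hold (invented times). TTH is 1 + 3 = 4 min under Section III and 3 min under Section V. It is 5 min under Section IV if the whole hold counts.

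If the hold counts, write TTH = 5 + E with E ≥ 0. A mean TTH of 5 requires the mean of E to be 0, so every E is 0 and the SD in that arm is 0, not 10. If TTH ends when bleeding stops, values below 5 are possible and this conflict does not arise.

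**The case against.** Section V is the outcome definition, and both arm descriptions in Section IV agree with it. Only Section III differs, so the start-time conflict is narrow and one correction removes it. That is fair, but no text gives Section V precedence, and Section III is itself a formal definition under the objectives.

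The power figures rest on an unsourced step length and on the 5 and 15 minutes being counted from compression. This stands. If they were set on the Section III clock, nothing is lost, and a step of 0.5 min still leaves power above 90%. Disc placement may also be a legitimate part of the time the StatSeal strategy takes. In that case the plan should say so.

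A reader might go further and infer that the discretion wording in Section IV lets an unblinded operator create a false difference. The documents do not support that. The sentence is identical in both arms, Sections III and V end TTH at the end of bleeding, and Section VI describes the extra compression as a response to oozing or bleeding. A bias would need operators to hold differently by arm for reasons other than bleeding. That is the general risk of an open comparison, could run in either direction, and has no figure in the documents.

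The case report forms are in an appendix not reproduced in the text reviewed and may already fix the time fields. They would not remove the contradiction from the protocol.

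**Conclusion.** The contradiction in the start of the primary outcome is established from the text. The Section III clock contains a step that only StatSeal patients have, and its effect is against the device. Whether the minimum hold counts after bleeding has stopped is unresolved. If it counts, the Section VI mean and SD cannot both hold in the StatSeal arm.

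The size is uncertain. Power of 91%, 88% or 79% for a step of 0.5, 1 or 2 min is an illustration that assumes 25 per arm, SD 10 and a 10-min difference from compression. A reader might infer that the trial is underpowered or that the sample-size arithmetic is wrong. Neither follows: the stated power is reproduced, and the loss disappears if the plan was sized on the Section III clock. This should be corrected, and preferably before more data are collected.

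**What to change.** 1. Reconcile Sections III, IV and V to one time zero, applied identically in both arms. The start of manual compression is already in Sections IV and V. Choosing it needs only a correction to Section III and removes the StatSeal-only step. If disc placement is meant to count, say so and size the trial on that clock.
2. State one stopping rule for the measurement in both arms, including whether the minimum hold counts once bleeding has stopped.
3. Make the mean and SD in Section VI consistent with that rule, and name the clock they refer to.
4. Record the times of Perclose deployment, start of compression and end of bleeding on the case report form, so that TTH is derived the same way for every patient.

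This changes what is measured and recorded. No hold length or other clinical rule is altered. The cost is a wording amendment and one or two extra time fields. One weakness remains: no blinding is described, so the judgment that bleeding has stopped may be made by someone who knows the arm.

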## **STUDY OVERVIEW GRAPHIC**

### **V. STUDY DEFINITIONS AND OUTCOMES**

#### Definitions of Baseline and Procedural Variables:

Smoking: Active smoking or >20 pack year tobacco history.

Diabetes: Hgb A1C >6.5% or active medical treatment for diabetes.

Hypercholesterolemia: LDL >130 or on treatment with antilipemic agents.

Hypertension: >140/80 or on medical treatment for hypertension.

Diagnostic procedure: Involving diagnostic catheters only.

Interventional procedure: Involving an interventional wire and therapeutic ACT typically >200, including for fractional flow reserve measurement where a stent is not placed.

Puncture attempts: Number of forward advances of the needle (not puncture sites) needed to achieve access

Procedure Start Time: Time when lidocaine is administered, prior to first puncture attempt.

Procedure End Time: Time when sheath is removed

#### Primary Efficacy Outcome:

- Total Time to Hemostasis (TTH), defined as from the time of manual compression after Perclose™ deployed until no further bleeding..

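### Time to hemostasis is read without masking and without common check times, so it can differ by arm when true hemostasis does not; the size could be negligible or large

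*Combined protocol and SAP*

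**What the plan says.** - **End of TTH.** Section V (Primary Efficacy Outcome) gives the interval as "defined as from the time of manual compression after Perclose™ deployed until no further bleeding". Section III ends it in similar terms: "beginning at the time at which the Perclose™ is deployed to the access site to when no additional bleeding is appreciated". Both endings are visual judgements. Neither names an assessor, a check time or a bleeding-free observation period.
- **Compression.** In section IV (Protocol), the control text reads "Manual pressure will be held for at least 5 minutes, the beginning of which will correspond to time point zero" and the StatSeal text "manual pressure will be held for at least 5 minute, the beginning of which will correspond to time point zero". Both set a minimum. Both then add: "Any manual compression needed or per protocol under the discretion of the operator will count towards the time to hemostasis".
- **Assignment.** Section IV randomizes after successful Perclose deployment. At that point "the envelope corresponding to that patient number in the Study Patient log will be pulled, opened, and the assignment revealed", and in the StatSeal arm the disc goes on the site under gauze.
- **When bleeding is seen.** Section VI explains the assumed SD as "additional time for manual compression if any site oozing/bleeding is seen after the initial compression".
- **Scheduled checks.** The timed site checks in sections III and V concern hematoma in recovery and on the ward. None concerns TTH in the catheterization laboratory.

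**The concern.** A site under manual pressure, with gauze and a disc over it in one arm, is hard to judge until pressure is eased. Section VI points the same way by placing the observation after the initial compression. TTH is then the time of the first check at which the site is dry, which is not the moment bleeding stopped. The recorded value depends on when someone chooses to look.

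That choice is made after the assignment is known. The plan expects 5 min with the patch and 15 min without it, so a natural tendency would be to check at the first permitted moment with the disc and somewhat later without it. Every control site already dry by the earlier time would then be recorded late. Neither randomization nor intention-to-treat analysis corrects this, because the difference enters through measurement after allocation. It would act on the primary outcome, probably in favour of the patch, and could not be repaired afterwards if check times were not recorded.

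**Working it through.** **Inputs from the plan (section VI unless noted):** 50 patients; 5 versus 15 min; SD 10 min; two-sided alpha 0.05; t test or Mann-Whitney; minimum hold 5 min (section IV). The allocation ratio is not stated; 1:1, 25 per arm, is assumed.

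**The plan's own figure.** The standardized difference is 10 / (10 × √(2/25)) = 3.54. Normal power is Φ(3.54 − 1.96) = Φ(1.58) = 94.2%; the noncentral t with 48 df gives 93.4%. The stated power of more than 90% reproduces, and this point does not change it.

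**Model for the concern (all assumed).** The true time T has the same distribution in both arms. TTH is the first check at or after T. Later checks come every 5 min. The StatSeal arm is first checked at 5 min; the control arm at 5, 10 or 15 min.

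**Spurious mean difference.** With a control first check at 10 min, only sites dry by 5 min are affected, and each gains 5 min:

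Difference = 5 × P(T ≤ 5)

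- Exponential, mean 5: 5 × 0.632 = 3.2 min
- Exponential, mean 10: 5 × 0.393 = 2.0 min
- Gamma, mean 15, SD 10: 5 × 0.124 = 0.6 min

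With a control first check at 15 min, the difference is 5 × [P(T ≤ 5) + P(T ≤ 10)]:

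- Exponential, mean 5: 5 × (0.632 + 0.865) = 7.5 min
- Exponential, mean 10: 5 × (0.393 + 0.632) = 5.1 min
- Gamma, mean 15, SD 10: 5 × (0.124 + 0.367) = 2.5 min

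**False-positive rates by simulation (t test / Mann-Whitney):**

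| True time | 5 vs 5 min | 5 vs 10 min | 5 vs 15 min |
|---|---|---|---|
| Exponential, mean 5 | about 5% / 5% | 75% / 97% | >99% / 100% |
| Exponential, mean 10 | about 5% / 4% | 13% / 36% | 58% / 89% |
| Gamma, mean 15, SD 10 | about 5% / 5% | 5% / 6% | 17% / 27–28% |

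The driver is the share of sites already dry at the earlier check: 63%, 39% and 12% in the three rows.

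**Which row is nearest the plan?** The gamma row takes the plan's control mean and SD as true times. The plan's 15 min is a recorded TTH, however, and recorded means exceed true means. Under the exponential with mean 10, a control first check at 10 min gives a recorded mean of 14.7 min. The planned 15 min therefore does not fix the row.

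**The case against.** The strongest objection concerns size. If the patch does nothing, both arms should behave like the plan's control group, at 15 min with SD 10. Taking those as true times, first checks at 5 versus 10 min barely move the error rate. This stands, and it is why the mean-5 figures cannot serve as the headline.

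The simulation also has every control patient checked late. Under the mean-5 exponential with a control first check at 7 min, rejection is about 15% (t test) and 70% (Mann-Whitney) if all controls are late, 7% and 26% if half are, and 6% and 10% if a quarter are. The full-shift difference there is only about 1 min, against a planned 10. This stands too.

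It can also be said that section VI implies the same sequence in both arms: hold, look, compress again only if bleeding. That helps, but a shared minimum is not a shared check time. The case report forms are not in the file, so a check grid there cannot be excluded.

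Two stronger readings are tempting. One is that the operator is documented as opening the envelope and declaring hemostasis. The documents name nobody for either task; they give the operator discretion over compression and describe no masking. The other is that the trial will produce a false positive for the patch. No section indicates that check times will differ by arm. The text permits the difference without making it certain, and reading bleeding only on release is an inference.

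**Conclusion.** The point holds as a weakness in how the endpoint is read. TTH has no common check times, the assignment is known before compression, and discretionary compression counts in the result, so an arm difference can arise without a true one.

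Its size is uncertain. For first checks at 5 versus 10 min, the spurious difference runs from about 0.6 to 3 min. The false-positive rate runs from about 5% to 75% (t test) and from 6% to 97% (Mann-Whitney). It is near nominal if most sites bleed well past the first check, and large if most are dry early and the arms are checked at systematically different times. True-time distributions, check times and 1:1 allocation are all assumed. The change is worth making because it is cheap and the bias cannot be undone later.

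This is separate from the start of the clock, where section III uses Perclose deployment and sections IV and V use the start of compression. Those passages must be reconciled, but doing so would leave the end of TTH unstandardized.

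**What to change.** In section IV (Protocol) and section V (Primary Efficacy Outcome):

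1. State one TTH assessment schedule that applies identically to both arms, with times chosen in advance by the investigators and consistent with the protocol's existing compression rule.
2. Record on the case report form the actual time and bleeding yes/no at every check, with the reason for any departure from the schedule.
3. Define TTH as the first check without bleeding.
4. Report first-check times by arm, so that a reader can see whether the schedule was kept equally. Departures remain possible, and this is the safeguard against their differing by arm.
5. State as a limitation that the bleeding judgement is unmasked. Common times do not address that.

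Compression remains a clinical decision; no hold or release time is proposed here. The cost is protocol wording, a short grid on the form and a slightly coarser TTH. Sample size and stated power are unchanged.
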